12.11 Overall Survival (OS)

OS is defined as the observed length of life from start of study treatment to death or the date of last contact.

12.12 Secondary Response Criteria - Immune-related Response Evaluation Criteria in Solid Tumors (irRECIST)

In 2013, Nishina et al. demonstrated that immune-related response criteria using unidimensional measurements were highly concordant with the bidimensional results of irRC, but with less measurement variability. ⁵⁵ Based on these findings and in order to utilize both the established criteria of irRC and RECIST 1.1, the two systems have been adapted, modified, and combined into the Immune-related Response Evaluation Criteria in Solid Tumors (irRECIST). The adapted irRECIST criteria are modifications to the irRC, incorporating the findings of Nishina et al. and the advantages of RECIST 1.1 while overcoming the shortcomings of each of the other guidelines.

irRECIST

Immune-related RECIST (irRECIST) guidelines according to Bohnsack et al. are presented below.

I. Baseline Assessments in irRECIST

In irRECIST, baseline assessment and measurement of measurable/non-measurable and target/non-target lesions and lymph nodes are in line with RECIST 1.1.

One new definition is added: If a subject has no measurable and no non-measurable disease at baseline the radiologist will assign 'No Disease' (irND) as the overall tumor assessment for any available follow-up time points unless new measurable lesions are identified and contribute to the total measured tumor burden (TMTB). irND is a valid assessment in studies with adjuvant setting where the protocol and study design allow the inclusion of subjects with no visible disease

Follow-up Assessments in irRECIST

A. Follow-up recording of target and new measurable lesions

The key difference in irRECIST is that the appearance of new lesions does not automatically indicate progression. Instead, all measured lesions (baseline-selected target lesions and new measurable lesions) are combined into the total measured tumor burden (TMTB) at follow up. Baseline-selected target lesions and new measurable lesions are

NOT assessed separately. Measurements of those lesions are combined into the TMTB, and one combined assessment provided.

In order to be selected as new measurable lesions (:5 2 lesions per organ, :5 5 lesions total, per time point), new lesions must meet criteria as defined for baseline target lesion selection and meet the same minimum size requirements of 10 mm in long diameter and minimum 15 mm in short axis for new measurable lymph nodes. New measurable lesions should be prioritized according to size, and the largest lesions elected as new measured lesions.

B. Follow-up non-target assessment

RECIST 1.1 definitions for assessment of non-target lesions apply. The response of non-target lesions primarily contributes to the overall response assessments of irCR and irNon-CR/Non-PO (irNN). Non-target lesions do not affect irPR and irSO assessments. Only a massive and unequivocal worsening of non-target lesions alone, even without progress in the TMTB is indicative of irPO. In alignment with RECIST 1.1, baseline selected non-target lesions can never convert to measurable lesions, not even if they increase in size at subsequent time points and become measurable. Only true new lesions can be measured and contribute to the TMTB.

C. Follow-up for New Non-Measurable Lesions

All new lesions not selected as new measurable lesions are considered new non-measurable lesions and are followed qualitatively. Only a massive and unequivocal progression of new non-measurable lesions leads to an overall assessment of irPO for the time point. Persisting new non-measurable lesions prevent irCR.

Overall Assessments for irRECIST

The irRECIST overall tumor assessment is based on TMTB of measured target and new lesions, non-target lesion assessment and new non-measurable lesions.

At baseline, the sum of the longest diameters (SumO) of all target lesions (up to 2 lesions per organ, up to total 5 lesions) is measured. At each subsequent tumor assessment (TA), the Sumo At each subsequent tumor assessment (TA), the Sumo of the target lesions and of new, measurable lesions (up to 2 new lesions per organ, total 5 new lesions) are added together to provide the total measurable tumor burden (TMTB). In the setting where treatment is continued beyond progression further assessments using irRECIST will use the first scan showing progressive disease as the new baseline scan to which all subsequent scans are compared.

Table 18. Overall Assessment by irRECIST

Complete Response (irCR)	Complete disappearance of all measurable
Complete Response (IICR)	and non-measurable lesions. Lymph nodes must decrease to < 10 mm in short axis.
Partial Response (irPR)	Decrease of 30% in TMTB relative to baseline, non-target lesions are irNN, and no unequivocal progression of new nonmeasurable lesions • If new measurable lesions appear in subjects with no target lesions at baseline, irPD will be assessed. That irPD time point will be considered a new baseline, and all subsequent time points will be compared to it for response assessment. irPR is possible if the TMTB of new measurable lesions decreases by 30% compared to the first irPD documentation • irRECIST can be used in the adjuvant setting, in subjects with no visible disease on CT/MRI scans. The appearance of new measurable lesion(s) automatically leads to an increase in TMTB by 100% and leads to irPD. These subjects can achieve a response if the TMTB decreases at follow-up, as a sign of delayed response. • Based on the above, sponsors may consider enrolling subjects with no measurable disease and/or no visible
	disease in studies with response related endpoints.
Stable Disease (irSD)	Failure to meet criteria for irCR or irPR in the absence of irPD
Progressive Disease (irPD)	Minimum 20% increase and minimum 5 mm absolute increase in TMTB compared to nadir, or irPD for non-target or new non-measurable lesions. Confirmation of progression is recommended minimum 4 weeks after the first

	irPD assessment. An irPD confirmation scan may be recommended for subjects with a minimal TMTB %-increase over 20% and especially during the flare time-window of the first 12 weeks of treatment, depending on the compound efficacy expectations, to account for expected delayed response. • In irRECIST a substantial and unequivocal increase of non-target lesions is indicative of progression. • IrPD may be assigned for a subject with multiple new non-measurable lesions if they are considered to be a sign of unequivocal massive worsening
Other	irNE: used in exceptional cases where insufficient data exist. irND: in adjuvant setting when no disease is detected irNN:, no target disease was identified at baseline, and at follow-up the subject fails to meet criteria for irCR or irPD

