6.0 CRITERIA FOR SUBJECT ELIGIBILITY

6.1 Subject Inclusion Criteria

Patients must fulfill all of the following criteria to be eligible for admission to the study:

- Male or female age 18 years at the time of informed consent
- Be willing and able to provide written informed consent/assent for the trial
- Be willing to comply with treatment protocol
- Subjects must have a histologically confirmed metastatic and/or locally advanced sarcoma
- Adequate performance status: ECOG O or 1/KPS 100-70%
- Subjects must have at least one prior line of systemic therapy (e.g. chemotherapy, immunotherapy, targeted or biological therapy) for their sarcoma. An exception to this criterion will be made for patients with sarcoma histological subtypes for which there is

no known standard systemic therapy (e.g., chondrosarcoma). Any patient that refuses standard chemotherapy for the treatment of their disease is also considered eligible. Prior adjuvant therapy will not count provided it was completed more than 6 months previously.

- Presence of measureable disease per RECIST v1.1.Target lesions must not be chosen from a previously irradiated field unless there has been radiographically and/or pathologically documented tumor progression in that lesion prior to enrollment.
- All subjects must agree to pre-treatment tumor biopsy. Subjects in whom biopsy is technically not feasible or in whom would result in unacceptable risk, in the opinion of the investigator, may be exempted from the biopsy requirement with discussion with the principal investigator.
- Adequate organ function determined within 21 days of treatment initiation, defined as per Table 2:

Table 2: Definition of Adequate Organ Function

System	Laboratory Value		
Hematological			
Absolute neutrophil count (ANC)	1,000 Imel		
Platelets	75,000 / mcl		
Hemoglobin	IB g/dl or 5.0 mmol/L		
Renal			
Serum creatinine OR	S1.5 X upper limit of normal (ULN) OR		
Measured or calculated [®] creatinine			
clearance	60 ml/min for subject with creatinine levels > 1.5 X		
(GFR can also be used in place of	institutional ULN		
creatinine or CrCl)			
Hepatic			
Serum total bilirubin	1.5 X ULN OR		
	Direct bilirubin s ULN for subjects with total bilirubin levels		
	> 1.5 ULN		
AST (SGOT) and ALT (SGPT)	s 2.5 X ULN OR		
AST (SGOT) and ALT (SGLT)	s 5 X ULN for subjects with liver metastases		
Albumin	2.5 mg/dl		
Coagulation			
	s1.5 X ULN unless subject is receiving anticoagulant		

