12.3.1 Primary Response Criteria (RECIST 1.1)

12.3.1.1 Evaluation of Target Lesions

Memorial Sloan Kettering Cancer Center IRB Number: 17-508 A(8)

Approval date: 07-May-2024

Complete Response (CR): Disappearance of all target lesions. Any pathological lymph nodes (whether target or non-target) must have reduction in short axis to <10 mm.

Partial Response (PR): At least a 30% decrease in the sum of the diameters of target lesions, taking as reference the baseline sum diameters.

Progressive Disease (PD): At least a 20% increase in the sum of the diameters of target lesions, taking as reference the smallest sum on study (this includes the baseline sum if that is the smallest on study). In addition to the relative increase of 20%, the sum must also demonstrate an absolute increase of at least 5 mm. (Note: the appearance of one or more new lesions is also considered progressions).

Stable Disease 1: Neither sufficient shrinkage to qualify for PR nor sufficient increase to qualify for PD, taking as reference the smallest sum diameters while on study.

12.3.1.2 **Evaluation of Non-Target Lesions**

Complete Response (CR): Disappearance of all non-target lesions and normalization of tumor marker level. All lymph nodes must be non-pathological in size (<10 mm short axis).

Non-CR/Non-PD: Persistence of one or more non-target lesion³³.

Progressive Disease (PD): Appearance of one or more new lesions and/or unequivocal progression of existing non-target lesions. Unequivocal progression should not normally trump target lesion status. It must be representative of overall disease status change, not a single lesion increase.

Although a clear progression of "non-target" lesions only is exceptional, the opinion of the treating physician should prevail in such circumstances, and the progression status should be confirmed at a later time by the review panel (or MSKCC Principal Investigator).

12.3.1.3 **Evaluation of Best Response**

The best response is the best response recorded from the start of the treatment until disease progression/recurrence (taking as reference for progressive disease the smallest measurements recorded since the treatment started). The patient's best response assignment will depend on the achievement of both measurement and confirmation criteria.

Table 18. Evaluation of Best Response - RECIST criteria

Target Lesions	Non- Target Lesions	New Lesions	Best Response	Best Response for This Category also Requires:
CR	CR	No	CR	4 wks. Confirmation

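### For patients treated beyond progression, Section 12.12 measures irRECIST response from the first PD scan, so a partial response can need less than a 30% fall from pre-treatment

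*Combined protocol and SAP*

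**What the plan says.** Section 12.12 sets out irRECIST as used in this trial. Baseline target lesions and new measurable lesions "are combined into the total measured tumor burden (TMTB) at follow up". Where treatment continues past progression, "further assessments using irRECIST will use the first scan showing progressive disease as the new baseline scan to which all subsequent scans are compared". That sentence names no lesion subgroup. It therefore covers any patient treated beyond progression, which Sections 9.3, 9.4, 12.1 and 13.0 allow.

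The overall-assessment table in Section 12.12 defines irPR as "Decrease of 30% in TMTB relative to baseline". A bullet in the same row deals with a special case: "If new measurable lesions appear in subjects with no target lesions at baseline, irPD will be assessed". It continues: "That irPD time point will be considered a new baseline, and all subsequent time points will be compared to it for response assessment". Section 6.1 requires "Presence of measureable disease per RECIST v1.1", so that bullet should describe nobody enrolled here.

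For RECIST 1.1, Section 12.3.1.3 closes the window for best response at progression: "The best response is the best response recorded from the start of the treatment until disease progression/recurrence". Section 12.12 has no equivalent sentence and does not adopt this one. The irRECIST response rate by 24 weeks is a secondary objective (Section 2.0) and a secondary endpoint (Section 14.2). Neither place names the reference scan or the response window.

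**The concern.** A PD scan usually shows more tumor than the pre-treatment scan. A 30% fall from it may be only a partial reversal of growth that took place on treatment. Counted as irPR, it carries the same label as a 30% fall from the pre-treatment burden, and the reported rate cannot tell the two apart.

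The irRECIST rate will be read beside the primary RECIST rate, and any excess is likely to be taken as delayed immune response. Some of that excess could come from the change of reference scan. Section 12.1 says that irRECIST is not used for treatment decisions, so the reset acts only on how irRECIST outcomes are classified.

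**Working it through.** **The plan's own figure.** Section 14.1 calls the treatment promising with 6 or more responders of 30. By exact binomial, P(X ≥ 6) is 0.0732 at a 10% response rate and 0.9234 at 30%. This agrees with the stated type I error of 0.07 and power of 92%. Both concern the RECIST 1.1 rate, and nothing below changes them. Section 14.2 attaches no test or target to the irRECIST rate.

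**Inputs.** irPR is a 30% fall in TMTB. Size-based PD is a rise of at least 20% and at least 5 mm over the nadir. New measurable lesions count in TMTB (all Section 12.12). New lesions alone are PD under RECIST 1.1 (Section 12.3.1). Scans fall at weeks 8, 16 and 24 (Section 12.1). The pre-treatment sum B = 100 mm is an assumption; the percentages do not depend on it.

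**Formulas.** Let P be the TMTB on the first PD scan.
- Threshold from pre-treatment: 0.70 × B = 70 mm.
- Threshold after the reset: 0.70 × P.
- Change from pre-treatment at the reset threshold: 0.70 × P/B − 1.
- Fall from the PD scan needed to reach 70 mm: (P − 70)/P. Under the reset it is always 30%.

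| PD-scan TMTB (mm) | Reset threshold (mm) | Change from pre-treatment | Fall from PD scan to reach 70 mm |
|---|---|---|---|
| 120 | 84 | −16% | 41.7% |
| 130 | 91 | −9% | 46.2% |
| 140 | 98 | −2% | 50.0% |
| 150 (targets 110 + two new 20 mm lesions) | 105 | +5% | 53.3% |
| 90 (nadir 75, then +20%) | 63 | −37% | 22.2% |
| 85 (targets 75 + one new 10 mm lesion, week 8) | 59.5 | −40.5% | 17.6% |

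**Direction.** The reset loosens the criterion when P is above B and tightens it when P is below B. Size-based PD at week 8 always loosens it, because the nadir is then the pre-treatment sum and P is at least 1.20 × B. It tightens after an earlier nadir, or when PD is by new lesions alone while the targets have shrunk (last two rows).

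**No net shrinkage.** Setting 0.70 × P = B gives P = B/0.70 = 142.9 mm. The PD scan must be at least 42.9% above pre-treatment.

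**Timing.** PD at week 8 leaves scans at weeks 16 and 24, enough for an irPR and its confirmation. PD at week 16 leaves only week 24 on the schedule, so it qualifies if confirmation is not required by week 24, or if an extra scan is done about 4 weeks after PD. Section 12.4 requires confirmation of response, but Section 12.12 does not say whether this applies to irPR.

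**Effect on the rate.** One patient is 1/30 = 3.3 points. The documents give no number of patients affected. For an assumed 0 to 3 patients, the shift is 0 to 10.0 points (3/30).

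**The case against.** The case on the other side is substantial, and several parts of it stand.

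- *The reset is an explicit rule, so nothing is contradicted.* This stands. A reader might infer that Section 12.12 conflicts with its own table, which describes a PD-scan baseline for patients without target lesions. But the table never says that the reset is confined to them, and no enrolled patient should fall under that bullet. A reader might also lean on the statement that baseline assessment and measurement of "lesions and lymph nodes are in line with RECIST 1.1". That concerns how lesions are classified and measured, and does not fix the reference scan after progression.
- *The only best-response window in the protocol closes at progression.* If it governs irRECIST too, responses after PD never enter the rate and the effect disappears. This is a fair reading, and the conclusion depends on its not applying. Against it, the window sits in the RECIST 1.1 section, and Section 12.12 gives instructions for comparing scans after PD.
- *Responses without net shrinkage are unlikely.* Largely accepted. Section 12.1 makes continued treatment depend on clinical stability, including no rapid progression, so growth of 42.9% or more followed by continued treatment should be uncommon. Thresholds between 70 and 100 mm do not need such growth.
- *The reset captures delayed response, which the protocol anticipates.* It is not needed for that. New lesions are absorbed into TMTB without automatic irPD, and a late fall to 70 mm or less counts against the pre-treatment scan anyway. Where the reset loosens the criterion, it adds only patients who did not reach that level.

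**Conclusion.** The concern holds as a poorly chosen reference rule for a descriptive secondary endpoint, and it is minor. Unless the until-progression window is carried over, a patient treated beyond PD can be an irRECIST responder by 24 weeks with less than a 30% fall from pre-treatment: 84 mm instead of 70 mm in the 120 mm example.

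Two further readings are tempting and are not supported. One is that the irRECIST rate must be inflated. The reset can move it either way, and the number of patients concerned is unknown. The other is that the trial's efficacy conclusion is affected. The primary RECIST rate and the 6-of-30 rule do not use irRECIST.

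The thresholds follow from the stated rules. The 100 mm sum, the example scans and the 0 to 3 patients are assumptions. Section 12.12 also leaves open whether the triggering progression is RECIST PD or irPD. Under either, a PD scan above the pre-treatment TMTB loosens the criterion. The example of tightening by new lesions alone needs RECIST PD.

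**What to change.** In Sections 12.12 and 14.2, state that irRECIST best response by 24 weeks is counted against the pre-treatment baseline. List separately the patients treated beyond PD and every response reached only against the PD-scan baseline, giving the pre-treatment, PD-scan and lowest later TMTB for each.

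Section 16.3 describes the study as completed, so the existing rule should not be silently replaced. Report both counts: the one under the Section 12.12 reset as prespecified, and the pre-treatment one labelled as specified after completion.

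The cost is wording in two sections and reclassification of measurements already taken in patients treated beyond PD. No scans, visits or patients are added, and the rules for stopping treatment do not change. The downside is that the irRECIST rate may come out slightly lower, or slightly higher where the reset had tightened the criterion.

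### Section 12.12 gives two conflicting rules for an irRECIST partial response, and the table's rule downgrades patients with no remaining non-target disease

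*Combined protocol and SAP*

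**What the plan says.** Best objective response by 24 weeks by irRECIST is a secondary objective (section 2.0) and a secondary endpoint (section 14.2). Neither place defines irPR, so section 12.12 is the only source for the rule.

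Section 12.12 addresses non-target lesions in several places:

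- The irPR row of the irRECIST table: "Decrease of 30% in TMTB relative to baseline, non-target lesions are irNN, and no unequivocal progression of new nonmeasurable lesions".
- The irSD row, which is the default: "Failure to meet criteria for irCR or irPR in the absence of irPD".
- The Other row, which explains the abbreviation: "irNN:, no target disease was identified at baseline, and at follow-up the subject fails to meet criteria for irCR or irPD".
- The text on follow-up of non-target lesions: "RECIST 1.1 definitions for assessment of non-target lesions apply"; then "The response of non-target lesions primarily contributes to the overall response assessments of irCR and irNon-CR/Non-PO (irNN"; then "Non-target lesions do not affect irPR and irSO assessments".

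The RECIST 1.1 category that the text imports is in section 12.3.1.2: "Non-CR/Non-PD: Persistence of one or more non-target lesion". Eligibility in section 6.1 requires "Presence of measureable disease per RECIST v1.1", and section 12.2.1 has measurable lesions recorded as target lesions at baseline.

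Some characters were altered when the PDF was read. I take irSO as irSD, Non-PO as Non-PD, and the irPR threshold as 30% or more. None of these is counted against the plan.

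**The concern.** There are two separate faults.

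First, the table makes the status of non-target lesions a condition of irPR, while the text says that status has no bearing on irPR. The plan does not say which takes precedence.

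Second, the condition is stated through an abbreviation that the section uses in two senses. One of them describes subjects without target disease, whom eligibility excludes. The other requires that a non-target lesion persists. Applied as written, that second sense withholds irPR from patients whose non-target disease has cleared or never existed, so a better non-target outcome yields a worse overall category.

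At stake is the irRECIST response rate: two careful readers could code the same scans differently. PFS by irRECIST should not change, because irPR and irSD are both non-progression and irPD is judged against the nadir, not against the response category.

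**Working it through.** The fault is one of wording, so the main check sets the rules side by side. Take an eligible patient, who therefore has target disease, with a fall in TMTB of at least 30%, residual target disease (so irCR is not met), and no progression of new non-measurable lesions. For each non-target state, ask whether irPR can be assigned.

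| Non-target state | A: irNN as in the Other row | B: irNN = Non-CR/Non-PD | C: text rule, no effect on irPR apart from irPD |
|---|---|---|---|
| None at baseline | no | no | yes |
| All disappeared (CR) | no | no | yes |
| Persisting (Non-CR/Non-PD) | no | yes | yes |
| Progressing (PD) | no | no | no |

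- **A** fails throughout because the Other row requires that no target disease was found at baseline.
- **B** fails in the first two rows because section 12.3.1.2 defines Non-CR/Non-PD as at least one non-target lesion persisting. With none, the condition is not met. There is no irPD, so the irSD row applies by default.
- **C** separates only progression from everything else.

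B and C differ in exactly two rows: no non-target lesions at baseline, and non-target CR with residual target disease. Every difference runs the same way, so the rate under B can never exceed the rate under C.

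**Size.** Let m be the number of patients in those two rows. With 30 evaluable patients:

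- rate under C − rate under B = m/30
- m = 1: 1/30 = 3.3 points
- m = 3: 3/30 = 10 points

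The documents do not give m. As an illustration on assumed inputs only, suppose 6 patients reach the TMTB threshold and 20% to 50% of them have no remaining non-target disease. Then m is 0.20 × 6 = 1.2 (about 1) to 0.50 × 6 = 3. The rate falls from 6/30 = 20% to between 5/30 = 16.7% and 3/30 = 10%. The 6 is borrowed from the primary success cutoff and is not a forecast; the 20% to 50% has no source in the plan.

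**Primary design.** The plan's own figures reproduce. For X binomial with n = 30, P(X ≥ 6) = 0.0732 at a 10% rate and 0.9234 at a 30% rate, matching the stated 0.07 and 92%. These concern response by RECIST 1.1, so the irPR wording does not enter them.

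**The case against.** The strongest reply is that the intent is clear. The text says non-target lesions do not affect irPR, and that only massive, unequivocal worsening of them gives irPD. Read with that, the irPR row merely excludes non-target progression, and an experienced reader would not send a patient with cleared non-target disease to irSD. This is a fair account of the probable intent. It works, however, by setting the table's stated condition aside, and nothing in the plan tells the person coding responses to do so.

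A reader might go further and infer from the Other row that no eligible patient can ever be an irRECIST partial responder (column A). The documents do not support that:

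- The text also uses irNN for irNon-CR/Non-PD, without any condition about target disease.
- The irPR row applies irNN to lesions, whereas the Other row describes a subject.
- A subject without target disease has no baseline sum from which TMTB could fall, and the irPR row deals with such subjects in a separate bullet, using the first irPD as the new baseline. Its main clause must therefore concern patients who have target lesions.
- The Other row entry has stray punctuation and may have lost words in extraction.

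In fairness to that reading, the text presents irNN as an overall assessment too, so the lesion-level sense has to be inferred. That supports calling the term ambiguous, but not calling irPR empty.

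The reply is also right that the endpoint carries no test or threshold, and that section 12.1 excludes irRECIST from treatment decisions.

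**Conclusion.** The point holds as a conflict within section 12.12. The irPR row and the text disagree on whether non-target status matters, and irNN has two meanings. On the more sympathetic of those meanings, the row still moves two kinds of patient from irPR to irSD: those with no non-target lesions, and those with non-target CR and residual target disease.

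The secondary irRECIST response rate can thus be understated, or depend on the sentence followed, by 3.3 points per affected patient. This assumes a denominator of 30. Whether any patient is affected cannot be known from the documents, so understatement is possible but not shown. The primary RECIST 1.1 design and treatment decisions are unaffected.

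A reader might also see a fault in the primary endpoint, because the RECIST Table 18 pairs target PR only with Non-CR/Non-PD non-target disease. That is an incomplete table and no more: section 12.3.1.1 defines target PR by the diameter sum alone, so the intent can be recovered.

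**What to change.** 1. Restate irPR in the irRECIST table as: TMTB reduced by 30% or more from baseline, criteria for irCR not met, and no irPD in non-target or new non-measurable lesions.
2. Amend the text to match: non-target lesions bear on irPR only through irPD.
3. Give irNN one meaning in both text and table. Editing only one of them leaves the conflict in place. If the Non-CR/Non-PD meaning is kept, the Other row entry can go, since no eligible patient can use it.
4. Section 16.3 describes the study as completed, so responses may already be coded. If so, record in an analysis note which rule was used, recheck patients in the two disputed groups from the recorded assessments, and report any change in the count.
5. As tidying only, complete the PR row of the RECIST Table 18 to cover target PR with non-target CR or with no non-target lesions.

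The cost is a few lines of wording and a recheck of existing records for a subset of at most 30 patients. No new data are needed, and the sample size and primary analysis stay as they are.
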